Secondary Analyses	
 All survival efficacy endpoints, e.g. time to relapse, relapse as a success/failure will be analysed by Cox proportional hazards and Kaplan Meier methodology. Binary endpoints, e.g. relapse/no relapse at 6 months, will be analysed by logistic regression. Other secondary efficacy endpoints will be summarised descriptively by treatment group. Safety data will be presented in tabular format and summarized descriptively according to GSK's Integrated Data Standards Library (IDSL) standards. Pharmacokinetic analyses will be detailed in a separate document. Pharmacogenetic data will be summarised and an exact logistic regression model will be used to assess the effect of derived CYP2D6 metabolizer class within treatment arm on relapse efficacy six months post-dosing. Healthcare resource use of P. vivax relapses and haemolysis events will be summarised descriptively.

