
 • Early failures who demonstrate initial clearance • Early failures who demonstrate initial clearance with genetically homologous infections • Early failures who demonstrate initial clearance with genetically heterologous infections • Early failures who demonstrate initial clearance with missing parasite genetics 
 • Listing of subjects considered early failures, together with their CQ and desethylCQ concentrations from the PK draw closest to the study day of recrudescence, and whether the infection is determined genetically homologous or heterologous (Listing 29).

Secondary Statistical Analyses
Endpoint(s)

 • Genetic classification by PCR of relapse infections occurring on or after Study Day 33 • See Section 13.6.4 for derivation of a relapse
Model Specification

 • No statistical model will be constructed; descriptive statistics only • mITT population
Model Results Presentation

 • Summary table (n and %) (Table 2.31) showing the proportion of subjects in each treatment group with P. vivax relapse infections classified as genetically heterologous or homologous • n will be the number of subjects with a relapse occurring on or after Study Day 33 • Bar chart of the percentage of subjects on each treatment arm with genetically heterologous or homologous infections, with 95% Wilson confidence intervals (Figure 2.5)

Secondary Statistical Analyses
Endpoint(s)

 Effect of CYP2D6 metabolism on relapse-free efficacy six months post-dosing within the treatment arms
Model Specification

 mITT population Logistic regression model adjusting for region and derived CYP2D6 metabolizer class within treatment arm (models fitted separately for each treatment arm) One-sided test at the 5% significance level (given published data indicating reduced CYP2D6 metabolism decreases PQ efficacy) Table 2.33: Poor Metaboliser (PM) and Intermediate Metaboliser (IM) vs Extensive Metaboliser (EM) and Ultra Metaboliser (UM) combined (PM vs EM+UM, IM vs EM+UM) Table 2.34: Intermediate Metaboliser vs Extensive Metaboliser (IM vs EM) (Rationale: the number of PMs and the number of UMs are expected to be small)
Model Results Presentation

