
 Number and percentage of subjects relapse free in each metaboliser class within each treatment arm Adjusted odds ratio, 90% CI and p-value

Secondary Statistical Analyses
Endpoint(s)

 Effect of qualitative CYP2D6 Activity Score (AS) on relapse-free efficacy six months post-dosing within the treatment arms
Model Specification

 mITT population Logistic regression model adjusting for region and qualitative CYP2D6 AS within treatment arm (models fitted separately for each treatment arm)
Model Results Presentation

 Table 2.35: degrees of freedom, wald chi-square and p-value of the type III effect of AS in the model

Additional Efficacy Summaries

 P. vivax asexual parasite counts (Table 2.1), mITT population: 
 Summary statistics (n, median, Q1, Q3, min and max) at each timepoint Other malarial asexual parasite counts (Table 2.2), P. vivax gametocyte counts (Table 2.3), other malaria gametocyte counts (Table 2.4), mITT population: 
 Summary statistics (n, median, Q1, Q3, min and max) at each timepoint Summary of subjects with P. vivax gametocyte emergence post baseline (n, %) (Table 2.28) Summary of subjects with P. falciparum asexual parasite emergence post baseline (n, %) (Table 2.32)

Efficacy Listings

 Efficacy data will be listed as presented in Appendix 14: List of Data Displays

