2.28.	mITT	SA23	Summary of P. vivax Gametocyte Emergence		SAC
2.29.	mITT	TTE7	Analysis of Recrudescence (Blood Stage Failure) Rates		SAC
2.30.	mITT	SA24a	Summary of Early Failures		SAC
2.31.	mITT	SA24b	Summary of Genetic Classification by PCR of Relapse Infections Occurring on or After Study Day 33		SAC
2.32.	mITT	SA25	Summary of P. falciparum Asexual Parasite Emergence	Change display to a listing if 5 or fewer subjects in total	SAC
CYP2D6					
2.33.	mITT	SA45	Analysis of Subjects with Relapse-Free Efficacy at 6 Months by CYP2D6 Metaboliser Class – Logistic Regression – PM and IM vs EM+UM		SAC
2.34.	mITT	SA45	Analysis of Subjects with Relapse-Free Efficacy at 6 Months by CYP2D6 Metaboliser Class – Logistic Regression – IM vs EM		SAC
2.35.	mITT	SA37	Effect of CYP2D6 Activity Score (AS) on Relapse-Free Efficacy at 6 Months – Logistic Regression		SAC

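### The RAP names exact logistic regression for CYP2D6 class in the synopsis but unqualified logistic regression in 8.1.2, and the choice can decide the poor-metaboliser result

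*Supplement*

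**What the plan says.** All references are to the current RAP (Amendment 1, 21-FEB-2017).

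- Synopsis, secondary analyses: "an exact logistic regression model will be used to assess the effect of derived CYP2D6 metabolizer class within treatment arm on relapse efficacy six months".
- Section 8.1.2, CYP2D6 metabolism: "Logistic regression model adjusting for region and derived CYP2D6 metabolizer class within treatment arm (models fitted separately for each treatment arm". The word exact does not appear.
- Appendix 14, title of Table 2.33: "by CYP2D6 Metaboliser Class – Logistic Regression – PM and IM vs EM+UM". Table 2.34 (IM vs EM) also carries the plain logistic label.
- Error rate and output in 8.1.2: "One-sided test at the 5% significance level", and "Adjusted odds ratio, 90% CI and p-value". No Wald, likelihood-ratio, score or exact test is named. The same table shows "Number and percentage of subjects relapse free in each metaboliser class within each treatment arm".
- On sparseness, 8.1.2 explains Table 2.34 with "Rationale: the number of PMs and the number of UMs are expected to be small".
- Wald is named elsewhere: for covariate and interaction testing (Table 2.22) and for the Activity Score logistic model (Table 2.35).
- Appendix 12 provides for alternative methods, with Fisher's exact test as its example, to be run in addition if a model is judged unsuitable. For logistic regression it mentions goodness of fit and residual plots. It does not mention separation or sparse cells.

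RAP 2.2 lists the CYP2D6 effect within arm as a secondary objective.

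**The concern.** One pre-specified test has two stated methods, and they can disagree sharply in the data pattern this analysis is most exposed to. The hypothesis is directional: reduced CYP2D6 activity should mean more relapse. With a handful of PMs in an arm, a strong effect can show itself as every PM relapsing. That is separation: the likelihood keeps rising as the PM coefficient grows, so there is no finite maximum-likelihood estimate, and a Wald statistic built on it collapses towards zero. An exact conditional test handles the same table without difficulty.

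A programmer working from 8.1.2 and the table titles could reasonably run a default logistic procedure; one working from the synopsis would run the exact version. At stake is the conclusion on PM vs EM+UM within each arm. Leaving the choice open also leaves it to be settled after the data are seen.

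**Working it through.** **The plan's own figure.** A one-sided 5% test uses z = 1.645, and so does a two-sided 90% interval. The stated alpha and CI agree. The plan gives no sample size, power or PM count for this analysis.

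**Inputs from the documents.** 251 randomised (Meta-Analysis Plan, Section 3) at 2:1 gives 251 × 2/3 ≈ 167 on TQ and 251/3 ≈ 84 on PQ. Background relapse is set at 30%, guided by 12/40 in the PQ+CQ arm of DETECTIVE Part 1 (Meta-Analysis Plan, 9.3), with a range of 15% to 35%.

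**Assumptions, not in the documents.** 1 to 6 PMs per arm, 30% IM, two regions of equal size, everyone genotyped and evaluable.

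**Wald inference when all PMs relapse.** Model: logit P(relapse) = β0 + β1·region + β2·PM + β3·IM. The PM likelihood term increases without limit in β2, while the PM information, Σp(1−p), goes to zero. The software stops at an arbitrary large value. Example, PQ arm with 5 PMs:

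- estimate 17.0, SE 1475.4, so z = 17.0/1475.4 = 0.0115 and one-sided p = 0.495
- 90% CI on the log scale: 17.0 ± 1.645 × 1475.4 = 17.0 ± 2427, effectively 0 to infinity as an odds ratio

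**Exact inference on the same kind of table, 3 PMs.** Region 1 has 2 PM, 13 IM and 27 EM+UM with 2, 4 and 8 relapses; region 2 has 1, 13 and 28 with 1, 4 and 8 relapses. A hand check, leaving IM out and stratifying by region:

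- region 1: 10 relapses among 29; both PMs among them: (10/29)(9/28) = 0.1108
- region 2: 9 relapses among 29; the PM among them: 9/29 = 0.3103
- product: 0.0344

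The full conditional model, which also conditions on the IM relapse total, gives 0.033.

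**All PMs relapsing, 30% background, one-sided p:**

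| PMs | Wald, PQ arm | Likelihood ratio, PQ arm | Exact, PQ arm (84) | Exact, TQ arm (167) |
|---|---|---|---|---|
| 1 | about 0.50 | 0.060 | 0.310 | 0.303 |
| 2 | about 0.50 | 0.014 | 0.095 | 0.094 |
| 3 | about 0.50 | 0.004 | 0.033 | 0.031 |
| 4 | about 0.50 | 0.001 | 0.012 | 0.010 |
| 5 | about 0.50 | 0.0005 | 0.0048 | 0.0036 |
| 6 | about 0.50 | 0.0002 | 0.0020 | 0.0011 |

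The Wald p stays at about 0.5 in both arms at every background rate from 15% to 35%.

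**Where the exact test starts to reject.** PQ arm: 2 PMs at 15% (p = 0.029), 3 at 20% (2 PMs give 0.057), 3 at 30%, 4 at 35% (3 PMs give 0.051). TQ arm: 2 PMs at 15% and 20% (0.029, 0.045), 3 at 25% to 35% (0.018, 0.031, 0.048). With one PM it never rejects.

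**How often all PMs relapse.** If each PM relapses with probability π, all k relapse with probability π^k. For k = 3 this is 0.9³ = 0.73, 0.7³ = 0.34 or 0.5³ = 0.13. Separation is therefore likely only if the true PM effect is large.

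**The case against.** The strongest reply is that the failing test is not written into the plan. Table 2.33 is never tied to Wald; that is an inference from software defaults and from Tables 2.22 and 2.35. Exact logistic regression is a kind of logistic regression, so 8.1.2 can be read as the general statement and the synopsis as the specific one. A likelihood-ratio p from the same fit would reject from two PMs at 30% background. This stands, and it makes the failure conditional. It also confirms that the p-value is undefined as written, and the likelihood-ratio route is not free: in a simulation with two PMs and no effect it rejected 7.3% of the time at nominal 5%, against 1.1% for an exact test.

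Second, Appendix 12 already offers an exact method, its list of checks is not presented as exhaustive, and the per-class counts would print 0% relapse-free among PMs beside an unbounded interval. This also stands in part. But nothing makes separation a trigger, the alternative is additional with no rule on which p-value governs, and Fisher's test would not adjust for region.

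Third, sparse PMs were foreseen: Table 2.34 exists for that reason, and the IM contrasts are not affected. The protocol claims only that null or intermediate metabolisers are at greater risk of relapse, not that all will relapse. Protocol 8.3.4.7 and RAP 13.6.6 also call the CYP2D6 genotype work exploratory, although RAP 2.2 lists the objective as secondary.

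A reader might infer that the plan will report the strongest possible evidence as no effect. The documents do not support that: it would need a Wald p-value, complete relapse among PMs, and a reader who ignores both the counts and the failed interval.

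**Conclusion.** The contradiction between the synopsis and 8.1.2 with Tables 2.33 and 2.34 is real and sits in the current RAP. Its practical effect is confined to the PM vs EM+UM contrast and depends on three things: that 8.1.2 is implemented with default Wald inference, that every PM in an arm relapses, and that there are enough PMs for the exact test to reject (about 3, or 2 to 4 over 15% to 35% background). Under those conditions the one-sided p is about 0.5 by one stated route and 0.033 or smaller by the other at 30% background in the PQ arm. With one or two PMs at about 30%, both routes fail to reject and the choice does not change the decision. PM count, IM share, region split and relapse rates are assumptions, so the probability that this bites cannot be given from the documents. It should be corrected because it can change the conclusion of a listed secondary objective and is cheap to settle before unblinding.

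**What to change.** In 8.1.2 and Table 2.33, state exact conditional logistic regression adjusted for region, as the synopsis does. Report an exact one-sided p-value and an exact 90% CI, with a median-unbiased odds ratio when the conditional estimate is infinite. In Appendix 12, add separation or sparse cells as a trigger and say which p-value governs. Table 2.34 (IM vs EM) may keep ordinary logistic regression if the synopsis is reworded to match and the test behind its p-value is named.

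The cost is a few lines of RAP text and one procedure option. The statistical price is somewhat conservative p-values (null rejection of 0.5% to 2.8% at nominal 5% in simulations of an exact region-stratified test) and wider intervals, confined to Table 2.33 if Table 2.34 is left as it is.

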8.2. Safety Analyses

The safety analyses will be based on the Safety population, unless otherwise specified.

Details of data displays are presented in [Appendix 14: List of Data Displays](#).

8.2.1. Overview of Planned Adverse Events Analyses

Counting of AEs will be based on the number of subjects – not the number of AEs. For example, if a subject reports the same AE on three occasions within the relevant time interval, that AE will only be counted once. If a subject experiences the same AE (i.e. same preferred term) more than once, they are counted only once under the count for the preferred term. If a subject experiences more than one AE in a particular SOC, they will only be included once in the count for the SOC, but will appear in the count for each appropriate preferred term within the SOC. Therefore, the sum of the numbers of subjects with each preferred term event within a SOC may exceed the total number of subjects with at least one event. For the summary of AEs by maximum intensity, subjects who experience the same event several times with different intensity will only be counted once with the maximum intensity.

Only treatment emergent AEs (TEAEs) will be presented as all subjects receive study medication on Study Day 1. TEAEs are defined as AEs with an onset date and time on or after that of the start of first dose of study medication (including CQ)

The occurrence of *P. vivax* malaria and any associated signs and symptoms are recorded as Disease Related Events (DREs) and will not be included in the AE data displays, but will be listed separately.

Adverse Events will be summarized by treatment group and as specified below and in [Appendix 14: List of Data Displays](#) and presented in order of descending frequency. [Table 2](#) provides an overview of the planned analyses, with further details of data displays being presented in [Appendix 14: List of Data Displays](#).

Table 2 Overview of Planned Adverse Event Analyses

Endpoint / Parameter/ Display Type	Absolute		
	Summary		Individual
	T	F	L
Adverse Events (AEs)			
All AEs			Y ¹
All Treatment Emergent AEs by SOC	Y		
All Treatment Emergent AEs by PT	Y		
Drug-related TEAE by PT	Y		
TEAEs by maximum intensity	Y		
Common (>=5% in any treatment group) TEAEs by PT	Y	Y ²	
Common (>=5% in any treatment group) Non-serious TEAEs by SOC and PT – number of subjects and occurrences	Y		
TEAEs by month of onset	Y		
Subject numbers for individual AEs			Y
Relationship between AE SOC, PTs and verbatim text			Y
Serious and Other Significant AEs			
Fatal TEAEs by PT	Y		Y
Serious TEAEs ³	Y		Y
Drug related serious TEAEs by PT	Y		
Drug related fatal serious TEAEs by PT	Y		
TEAEs leading to withdrawal from the study	Y		Y
TEAEs leading to discontinuation from study treatment	Y		
AEs that are considered to be haematologically-related (i.e. clinically relevant drops in Hb or Hct or other complications)	Y		
Grade 3 and Grade 4 AEs by PT	Y		
Disease Related Events			Y

NOTES:

- T = Table, F = Figures, L = Listings, Y = Yes display generated, SOC = System Organ Class, PT = Preferred Term.
- Summary = Represents TF related to any summaries (i.e. descriptive statistics) of the observed raw data.
- Individual = Represents FL related to any displays of individual subject observed raw data.
- Treatment emergent AEs (SAEs) are defined as AEs (SAEs) with an onset date and time on or after that of the start of first dose of study medication (including CQ).
- AEs which have missing onset dates and any with an onset date equal to that of medication, but where onset time is unknown, will be considered to be treatment emergent.
- For each preferred term counting will be done by subject and not event.
- AEs related to drug will be selected based on where the 'Relationship to Investigational Product' flag on the eCRF has been marked 'Yes'.
- See Section 13.6.3 for additional information on the derivations and definitions of AEs
- Additional information on any deaths will be provided by Global Clinical Safety and Pharmacovigilance (GCSP) as part of the SAE reconciliation process.
- Events will be sorted based on Total incidence unless otherwise noted in Section 13.14.6
- ¹ Treatment Emergent AEs will be flagged
- ² Plot of common AEs and relative risk will be generated.
- ³ By SOC, by overall frequency and by SOC – number of subjects and occurrences

8.2.1.1. Pregnancies

Any pregnancies occurring will be discussed in the Clinical Study Report.

8.2.1.2. Patient Profiles of Cardiovascular Events and Deaths

Additional information collected on cardiovascular events and deaths will be reported in Patient Profiles for inclusion in the CSR. One profile per subject with an event will be produced using IDSL patient profile display standards.

8.2.2. Overview of Planned Clinical Laboratory Analyses

Table 3 provides an overview of the planned analyses, with further details of data displays being presented in Appendix 14: List of Data Displays.

Table 3 Overview of Planned Clinical Laboratory Analyses

Endpoint / Parameter/ Display Type	Absolute			Change from BL		
	Summary		Individual	Summary		Individual
	T	F	L	T	F	L
Chemistry						
Chemistry Data by Treatment and Time	Y	Y ¹				
Chemistry Changes from Baseline				Y	Y	
Chemistry Laboratory Abnormalities ²	Y	Y	Y			
Haematology						
Haematology Data by Treatment, Time and Sex	Y	Y				
Haematology Changes from Baseline by Treatment, Time and Sex				Y	Y	
Haematology Laboratory Abnormalities ²	Y	Y	Y			
Haemoglobin Categories ⁴ of Change from Baseline by Treatment and Time				Y		
Haemoglobin Categories ⁴ of Change from Baseline by Treatment, Time and Sex				Y		
Maximum Fall in Haemoglobin Over First 29 Days ⁴					Y	
Mean Change in Haemoglobin Over First 29 Days ⁴				Y	Y	
Urinalysis						
Urine Concentration			Y			
Urinalysis Dipstick Results	Y		Y			
Hepatobiliary (Liver)						
Liver Monitoring/Stopping Event Reporting	Y		Y			
Liver Biopsy Details	Y		Y			
Liver Imaging Details	Y		Y			
Medical Conditions for Subjects with Liver Stopping Events			Y			

Endpoint / Parameter/ Display Type	Absolute			Change from BL		
	Summary		Individual	Summary		Individual
	T	F	L	T	F	L
LFT Abnormalities		Y				
Maximum LFTs		Y				
LFT Changes from Baseline		Y				

NOTES:

- T = Table, F = Figures, L = Listings, Y = Yes display generated
- Summary = Represents TFL related to any summaries (i.e. descriptive statistics) of the observed raw data.
- Individual = Represents FL related to any displays of individual subject observed raw data.
- ¹ Boxplots by treatment, time and gender for total bilirubin and indirect bilirubin
- ² Abnormalities refer to values outside of the clinical concern range (F3) as defined in Section 13.8.1.
- ³ G6PD enzyme activity only
- ⁴ Categories defined as ≤ 20 g/L, > 20 g/L to ≤ 30 g/L, > 30 g/L
- ⁵ See Section 8.2.2.1
- All scheduled visits should be included in the tables and figures.
- Data recorded at unscheduled assessments will not be included in tables and figures but will be listed.
- Change from baseline is defined in Section 13.5.2.

8.2.2.1. Haemoglobin Declines and Related Laboratory Parameters

For all subjects with a drop in haemoglobin > 20 g/L, G6PD enzyme activity will be plotted against maximum drop in haemoglobin up to and including the Day 29 visit, with separate pages for each treatment group (Figure 3.35). Within the plot, different symbols will be used for the following categories:

- subjects who were genotyped and had a mutation classified as World Health Organization (WHO) class 1
- subjects who were genotyped and had a mutation classified as WHO class 2
- subjects who were genotyped and had a mutation classified as WHO class 3
- subjects who were genotyped and had a mutation of unknown significance
- subjects who were genotypically normal or had a mutation classified as a normal variant (WHO class 4)
- subjects who were not genotyped or did not have an evaluable genotyping result

A second plot will include only females with a drop in haemoglobin > 20 g/L (Figure 3.36), with separate pages for each treatment group, and a third for G6PD deficient males only (Figure 3.37).

A further set of plots will be produced for each treatment group for all subjects with non-missing G6PD genotype results, with males and females plotted on separate pages. Mean change from baseline haemoglobin will be plotted for G6PD normals by visit, up to and including Day 60 (Figure 3.38). Error bars will be plotted at each time point. Mean change from baseline haemoglobin for G6PD deficient males will also be plotted on the same

graph. It is anticipated that the number of G6PD deficient subjects will be very low, so all change from baseline values will be plotted for all G6PD-deficient subjects, but no error bars will be produced.

A further plot by treatment group will display mean change from baseline haemoglobin for all male subjects where G6PD genotype is unknown (Figure 3.39). This plot will cover all visits up to and including Day 29. Error bars will be plotted at each time point.

If a subject has a >20g/L decline from baseline haemoglobin or is a female who was genotyped and found to be G6PD deficient, a haematological profile plot will be produced for the subject (Figure 3.41). This will display their haemoglobin, absolute reticulocyte, methaemoglobin and bilirubin results (total and indirect bilirubin on same plot) at each visit. The subject ID, treatment group, sex, age and G6PD status should be included as a header for each subject's plot.

A summary of haemoglobin declines of the first 29 days by treatment (Table 3.30) and by treatment and sex (Table 3.31) will also be produced.

A listing of all G6PD deficient subjects will be produced including their drop in haemoglobin, G6PD mutation, and their haemoglobin data over time (Listing 31).

Patient profile plots of G6PD for G6PD deficient females will be produced (Figure 3.43). Boxplots by visit and treatment group will also be produced for G6PD enzyme activity (Figure 3.29) and change from baseline in G6PD enzyme activity (Figure 3.30). G6PD will be presented in IU/gHB,

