Methemoglobinemia (MetHb)	Methemoglobinemia has been observed in previous studies associated with larger total doses of TQ than are being considered for clinical investigation. Risk factors have been assessed and include a strong relationship between MetHb development, TQ dose, and body surface area.	Methemoglobinemia will be monitored instream. Data will be collected to support tolerance in female heterozygous carriers of G6PD deficiency. An assessment will be made to determine if there is any relationship between Hb decline and Methb.
Retinal Toxicity	
No ophthalmological changes have been observed with TQ in preclinical species or in any of the TQ-treated subjects in previous studies.
 
Irreversible retinopathy has been reported with the combination partner CQ. The effects with CQ are dose related and have been observed following cumulative total doses of >1g base/kg body weight. CQ dose used in treatment of P. vivax is a total of 25mg/kg over 3 days. Retinopathy associated with severe malaria is reported in the literature.
	In a subset of the study population, anatomical and functional ophthalmic tests will be conducted, including digital retinal photo and macular function test (Humphrey 10-2 visual field). Assessments will be taken at baseline (Day 1), Day 29 and Day 90 of the study. For any abnormality subjects will be followed for outcome.

Potential Risk of Clinical Significance	Data/Rationale for Risk	Mitigation
Keratopathy	
No ophthalmological changes were observed in preclinical species.
 
Reversible vortex keratopathy was observed in previous TQ clinical trials.
	
Appropriate sites will conduct slit lamp procedure and be provided with standardized photos of keratopathy to capture grades of keratopathy consistently. Assessments will be taken at baseline (Day 1), Day 29 and Day 90 of the study.

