8.3.4.7. Exploratory G6PD & CYP-2D6 Genotype Analyses

All treated female and any male subjects meeting the pre-specified criteria for Hb deficiency (Hb decrease $\geq 30\%$ or ≥ 3.0 g/dL, or an overall drop below 6 g/dL) will be examined for mutations in the G6PD gene to investigate the relationship between G6PD

enzyme level, Hb and genotype. Genetic strategies most likely to be used include single nucleotide polymorphism (SNP) genotyping and/or direct DNA sequencing of subject DNA samples. The same genetic approaches may be used to investigate G6PD genotype in subjects that do not meet the pre-specified criteria for G6PD deficiency to allow relationships between G6PD enzyme level, Hb and genotype to be explored.

In addition, exploratory CYP-2D6 genotype analyses will be undertaken to test the hypothesis that null and/or intermediate metabolisers of 8-aminoquinoline drugs are more at risk of *P. vivax* relapse [Bennett, 2013].

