3.23.	Safety	LB9	Boxplot of Clinical Chemistry Parameters by Visit and Treatment Group – Creatine Kinase		SAC

Safety : Figures					
No.	Population	IDSL / TST ID / Example Shell	Title	Programming Notes	Deliverable
3.24.	Safety	LB9	Boxplot of Clinical Chemistry Parameters by Visit and Treatment Group – Urea		SAC
3.25.	Safety	LB9	Boxplot of Clinical Chemistry Parameters by Visit and Treatment Group – Creatinine		SAC
3.26.	Safety	LB9	Boxplot of Clinical Chemistry Parameters by Visit and Treatment Group – Alkaline Phosphatase		SAC
3.27.	Safety	LB9	Boxplot of Clinical Chemistry Parameters by Visit and Treatment Group – Alanine Amino Transferase		SAC
3.28.	Safety	LB9	Boxplot of Clinical Chemistry Parameters by Visit and Treatment Group – Aspartate Amino Transferase		SAC
3.29.	Safety	LB9	Boxplot of Clinical Chemistry Parameters by Visit and Treatment Group - G6PD enzyme activity		SAC
3.30.	Safety	LB9	Boxplot of Change from Baseline in Clinical Chemistry Parameters by Visit and Treatment Group - G6PD enzyme activity		SAC
3.31.	Safety	LB9	Boxplot of Total Bilirubin by Visit and Treatment Group – Males		SAC
3.32.	Safety	LB9	Boxplot of Total Bilirubin by Visit and Treatment Group – Females		SAC
3.33.	Safety	LB9	Boxplot of Indirect Bilirubin by Visit and Treatment Group – Males		SAC
3.34.	Safety	LB9	Boxplot of Indirect Bilirubin by Visit and Treatment Group – Females		SAC
3.35.	Safety	SF1	Maximum Fall in Haemoglobin over First 29 Days by Enzyme Activity and Treatment Group	Subjects with decline of >20g/L in haemoglobin only	SAC

Safety : Figures					
No.	Population	IDSL / TST ID / Example Shell	Title	Programming Notes	Deliverable
3.36.	Safety	SF1	Maximum Fall in Haemoglobin over First 29 Days by Enzyme Activity and Treatment Group - Females	Subjects with decline of >20g/L in haemoglobin only	SAC
3.37.	Safety	SF1	Maximum Fall in Haemoglobin over First 29 Days by Enzyme Activity and Treatment Group – G6PD Deficient Males	Subjects with decline of >20g/L in haemoglobin only	SAC
3.38.	Safety	SF2	Mean Change from Baseline in Haemoglobin by Treatment Group, Visit and G6PD status (Subjects with Known G6PD Genotype)		SAC
3.39.	Safety	SF2	Mean Change from Baseline in Haemoglobin by Treatment Group and Visit (Male Subjects with Unknown G6PD Genotype)		SAC
3.40.	Safety	LB11	LFT Profile Plots	Only for subjects with >3 ULN in ALT or AST. Add footnote to this effect. The subject ID, treatment group, sex, age and race should be included as a header for each subject's plot.	SAC

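### The only plots of G6PD activity against haemoglobin fall admit only falls above 20 g/L, so they cannot show how the fall varies with activity across all subjects

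*Supplement*

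**What the plan says.** RAP Amendment 1, section 8.2.2.1, defines Figure 3.35 as follows: "For all subjects with a drop in haemoglobin > 20 g/L, G6PD enzyme activity will be plotted against maximum drop in haemoglobin", up to the Day 29 visit, one page per arm, with symbols for WHO mutation class. Figure 3.36 applies the same threshold to women, and Figure 3.37 covers G6PD-deficient men. In the display list (Appendix 14, section 13.14.7) all three carry the title "Maximum Fall in Haemoglobin over First 29 Days by Enzyme Activity and Treatment Group" and the programming note "Subjects with decline of >20g/L in haemoglobin only".

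The same section plans displays that are not cut on the fall:

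- Figure 3.38: "A further set of plots will be produced for each treatment group for all subjects with non-missing G6PD genotype results". It shows haemoglobin change by visit and genotype status, with individual values for deficient subjects.
- Listing 31: deficient subjects, with their fall, mutation and haemoglobin over time.
- Figure 3.43: enzyme-activity profiles for deficient women.

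The individual profiles in Figure 3.41 include genotyped-deficient women regardless of fall. Everyone else enters only under the condition "If a subject has a >20g/L decline from baseline haemoglobin".

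Protocol Amendment 5, section 8.3.4.7, plans mutation testing in treated women and in certain men to investigate how enzyme level, haemoglobin and genotype relate. It permits extension to further subjects "to allow relationships between G6PD enzyme level, Hb and genotype to be explored". Protocol Table 1 (section 1.3.1), in the methaemoglobinaemia row, adds: "An assessment will be made to determine if there is any relationship between Hb decline and Methb".

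**The concern.** The threshold is applied to one of the two plotted variables, and that variable is the outcome. A subject with low enzyme activity and a small fall is left out, and so is a subject with normal activity and a small fall. This has two consequences.

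- Among those plotted, any true gradient of fall on activity looks shallower than it is.
- The figure shows who fell by more than 20 g/L but not how many at the same activity level did not. The proportion with a large fall at a given activity cannot be read from it.

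This matters more because RAP section 2.1 drops the incidence estimate for women with moderate deficiency, for want of recruits. The relation on the continuous activity scale is one of the few remaining ways to use the quantitative assay result. A flat or sparse Figure 3.35 could be taken as a sign that activity matters little, when the selection alone can produce that picture.

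**Working it through.** The plan gives no figure for these displays, so there is nothing to reproduce. The check has three steps.

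**1. Does any other display do the job?** Going through RAP 8.2.2, 8.2.2.1 and Appendix 14:

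- Figures 3.35 to 3.37: activity against maximum fall, all cut at 20 g/L.
- Figures 3.38 and 3.39: haemoglobin change by genotype status (known; unknown in men). No activity axis.
- Figures 3.29, 3.30 and 3.43: enzyme activity alone.
- Figure 3.41: individual profiles of selected subjects.
- Listing 31: deficient subjects only. Mutation and haemoglobin are named, activity is not.
- Tables 3.25 to 3.31: haematology by treatment, time or sex.

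None sets activity against fall for all subjects.

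**2. How many subjects would be plotted?** Inputs: protocol 3.3.1 reports that on TQ 300 mg in phase II about 30% fell by 1.5 to 2.5 g/dL and 4% by more than 2.5 g/dL, with similar falls in the other groups. The meta-analysis plan (section 3) gives 251 randomised. I assume that the phase II shares carry over to both arms here.

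Everyone above 25 g/L is above 20 g/L, and nobody below 15 g/L is. So the share lies between 4% and 30% + 4% = 34%:

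- 0.04 × 251 = 10
- 0.34 × 251 = 85

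At least 251 − 85 = 166 subjects, about two-thirds, are left out whatever the shape of the distribution.

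For a point inside that range, fit a normal distribution to P(>15) = 0.34 and P(>25) = 0.04:

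- SD = 10 / (1.751 − 0.412) = 7.47 g/L
- mean = 25 − 1.751 × 7.47 = 11.9 g/L
- c = (20 − 11.9) / 7.47 = 1.08, so P(>20) = 0.140
- 0.140 × 251 = 35 plotted, about 86% omitted

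**3. How much does the selection flatten the relation?** Under bivariate normality, keeping only fall > 20 g/L shrinks the variance of the fall by v = 1 − λ(λ − c), where λ is the normal density at c divided by 0.140, or 1.59. So v = 1 − 1.59 × (1.59 − 1.08) ≈ 0.19. For a full-sample correlation of size ρ:

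- correlation among those plotted = ρ√v / √(1 − ρ² + ρ²v)
- slope of fall on activity, relative to the full sample = v / (1 − ρ² + ρ²v)

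The documents give no ρ, so a range is assumed:

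| assumed ρ | ρ among plotted | slope retained |
|---|---|---|
| 0.3 | 0.14 | 21% |
| 0.5 | 0.24 | 24% |
| 0.7 | 0.39 | 31% |

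A simulation of 1,000,000 draws gave the same values to the precision shown.

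**The case against.** The strongest reply is that the section describes subjects who had a decline. The figures are case displays with mutation symbols, and the RAP plans no slope, correlation or test for them. It tests no hypothesis even for the primary endpoint (sections 2.4 and 7.1.2). This stands in part. A statement about lost power would describe a test that nobody planned, so none is made here. But the figures are the only place where activity meets fall, and readers will use them that way. Highlighting large falls is a fair purpose, and a reference line on an all-subject plot still serves it.

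A reader might infer that deficient subjects with small falls vanish from the report. The documents do not support that: Figure 3.38, Listing 31 and, for women, Figures 3.41 and 3.43 show them whatever their fall. What is missing is activity against fall across everyone, normal subjects included.

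Protocol 8.3.4.7 is headed exploratory, and its extension to further subjects is permissive, so leaving it undelivered is not a breach of a firm commitment. The RAP also expects very few deficient subjects, and entry rules exclude men below 70% and women below 40% of the site median. An all-subject plot will therefore still be thin at low activity. Both points stand and limit what the change can yield.

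On methaemoglobin, Table 1 names no method or population. The RAP box-plots it and haemoglobin separately for all subjects and pairs them in Figure 3.41. That makes an added plot optional.

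**Conclusion.** The concern holds as a modest one. Figures 3.35 to 3.37 are selected on the outcome that they plot. They cannot show how fall varies with activity across the trial population, or the proportion with a large fall at a given activity. A weakened association among subjects above 20 g/L could still be visible.

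The number plotted is best given as a range of about 10 to 85 of 251. The figure of 35 is one point in it and rests on a normal fit and on carrying phase II shares over. The direction of the flattening does not depend on those choices. Its size does, and also on correlations that the documents do not supply. Phase II falls were similar across groups and judged disease-related, which gives no support for a strong correlation here.

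A reader might go further and conclude that the trial's haemolysis result is compromised. It is not: the primary comparison of clinically relevant haemolysis uses the Safety population and does not involve this filter.

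**What to change.** In RAP 8.2.2.1 and the Appendix 14 entries for Figures 3.35 and 3.36:

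- Plot every Safety-population subject (all women for 3.36) with a baseline G6PD value and at least one post-baseline haemoglobin to Day 29, by arm.
- Draw a reference line at 20 g/L and keep the genotype symbols, so that large falls still stand out.
- Put activity on the scale of percentage of site median, which RAP 13.6.2 already derives. Site medians run from 7.17 to 9.01 IU/g Hb, a ratio of 9.01 / 7.17 = 1.26, so absolute values are not directly comparable between sites.
- Give a descriptive slope or rank correlation of maximum fall on that scale, by arm, with a 95% CI and no test. State in a footnote how many subjects lie below 70%.

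Optionally, add an all-subject plot of maximum methaemoglobin against maximum haemoglobin fall, to meet the assessment mentioned in protocol Table 1.

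The cost is a few lines of RAP text, one changed programming filter and a short statistic per arm. All data are already collected, and no clinical rule is touched.
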